### **6.1.2. RMC-4630 and Osimertinib (Study in US Only)**

During the Dose Escalation Component, RMC-4630 will be administered orally on an intermittent basis with twice weekly dosing on D1 and D2 with a starting dose of 140 mg. Alternative dose schedule for RMC-4630 including D1D4 dosing may be explored depending on emerging data from this study and other RMC-4630 studies. Osimertinib will be dosed orally on the approved monotherapy dose and schedule of 80 mg once daily. The tablets and capsules should not be crushed or chewed. The participant should administer the study intervention approximately the same time every day except for clinic visit days as listed in the SoA (Section 1.3).

Dosing in the Dose-Expansion Component of RMC-4630 will be determined from the respective Dose-Escalation Component.

The participant is expected to administer a dose twice weekly on D1 and D2 (or D1D4 if an alternative schedule is implemented) except clinic visit days as listed in SoA. On these clinic visits, the participant should await instruction from the study staff to coordinate with the timing of PK and/or biomarker sampling.

**Table 7 Study Interventions Administered: RMC-4630 and Cobimetinib**

Component Name	Dose-Escalation and Dose-Expansion
Intervention Name	RMC-4630 and Cobimetinib
Type	Drugs
Dose Formulation	RMC-4630: [REDACTED] Cobimetinib: Film-coated Tablet
Unit Dose Strength(s)	[REDACTED] [REDACTED]
Dosage Level(s)	[REDACTED] [REDACTED] [REDACTED] [REDACTED] [REDACTED] [REDACTED] [REDACTED]
Route of Administration	Oral with water after 1 hour fast; no food or drink (other than water) allowed for 1 hour after administration for RMC-4630 alone or RMC-4630 in combination with cobimetinib. No restrictions for cobimetinib when taken alone
Investigational Product	RMC-4630 Cobimetinib
Sourcing	RMC-4630 [REDACTED] [REDACTED] Cobimetinib: Supplied by Roche
Packaging and Labeling	[REDACTED] Cobimetinib: Supplied as 63-count in HDPE bottles, overlabeled
Current/Former Name(s) or Alias	RMC-4630, [REDACTED] COTELLIC®, cobimetinib, cobimetinib fumarate

Abbreviations: CMO, contract manufacturing organization; HDPE, high-density polyethylene; PIC, powder-in-capsule.

**Table 8 Study Interventions Administered: RMC-4630 and Osimertinib**

Component Name	Dose-Escalation and Dose-Expansion
Intervention Name	RMC-4630 and Osimertinib
Type	Drugs
Dose Formulation	RMC-4630: [REDACTED] Osimertinib: Film-coated Tablet
Unit Dose Strength(s)	[REDACTED] [REDACTED]
Dosage Level(s)	[REDACTED] [REDACTED] [REDACTED]
Route of Administration	Oral with water after 1 hour fast; no food or drink (other than water) allowed for 1 hour after administration for RMC-4630 alone or RMC-4630 in combination with osimertinib. No restrictions for osimertinib when taken alone
Investigational Product	RMC-4630 Osimertinib
	RMC-4630: [REDACTED] [REDACTED] Osimertinib: Commercially available via pharmacy
Packaging and Labeling	RMC-4630: Study drugs (PIC drug products) are packaged in [REDACTED] [REDACTED] Osimertinib: Supplied as 30-count in HDPE bottles
Current/Former Name(s) or Alias	RMC-4630, RMC [REDACTED] TAGRISSO®, osimertinib, osimertinib mesylate, mereletinib

Abbreviations: CMO, contract manufacturing organization; HDPE, high-density polyethylene; PIC, powder-in-capsule; QD, daily.

## 6.2. Preparation/Handling/Storage/Accountability

RMC-4630 [REDACTED] are packaged in high-density polyethylene (HDPE) bottles with open labeling and are shipped and stored [REDACTED]

Cobimetinib (COTELLIC®) is shipped and stored [REDACTED]

Osimertinib (TAGRISSO®) is shipped and stored at 15°C to 30°C (59-86°F).

The investigator or designee must confirm appropriate temperature conditions have been maintained during transit for all study intervention received and any discrepancies are reported and resolved before use of the study intervention.

Only participants enrolled in the study may receive RMC-4630 or cobimetinib and only authorized site staff may supply study intervention. Osimertinib will be supplied by the local pharmacy. All study intervention must be stored in a secure, environmentally controlled, and monitored (manual or automated) area in accordance with the labeled storage conditions with access limited to the investigator and authorized site staff.

The investigator, institution, or the head of the medical institution (where applicable) is responsible for study intervention accountability, reconciliation, and record maintenance (ie, receipt, reconciliation, and final disposition records).

Further guidance and information for the final disposition of unused study interventions are provided in the study Pharmacy and Investigational Product Administration Manual.

### **6.3. Measures to Minimize Bias: Randomization and Blinding**

This is an open-label study without randomization. In order to minimize bias, the participants will be assigned sequentially as they are enrolled into the study using the inclusion and exclusion criteria as outlined in [Section 5.1](#) and [Section 5.2](#). Enrollment will be confirmed by the sponsor Medical Monitor after review of all supporting documentation for eligibility criteria.

The following guidelines will be considered for enrollment and cohort assignment for participants enrolled in the RMC-4630 and cobimetinib cohort:

- Once the Dose-Expansion Component commences, enrollment into the Dose-Escalation cohort will have priority over the Dose-Expansion cohort
- For parallel Dose-Escalation cohorts slot assignment will be completed in an alternating manner
- For parallel Dose-Expansion cohorts below the RP2D, slot assignment will be completed in an alternating manner, taking into account that each cohort aims to have 50% of participants have [REDACTED]
- In the Dose-Expansion Cohort at the RP2D, participants will be stratified based on histotype/genotype. If more than one mutation is present, participants will be stratified into the genotype with the lowest enrollment.
- Sites may enroll participants into the Dose-Expansion Component if there is no Dose-Escalation Cohort open for enrollment ([Appendix 9A](#))

Participants will be allocated a screening number at the time of signing the informed consent form (ICF). If a participant is a screen failure, the number will not be reassigned.

## 6.4. Study Intervention Compliance

### 6.4.1. Compliance Instructions

Dosing instructions will be provided to the participant, and participant compliance with study intervention will be reviewed at each visit. Compliance will be assessed by counting returned capsules (RMC-4630) and tablets (cobimetinib), in conjunction with participant diary information and participant questioning. Since Osimertinib is supplied as part of Standard of Care by local pharmacies, compliance will only be assessed by reviewing participants' diaries and questions asked during clinic visits. Refer to [Section 8.4](#) in the event a participant is suspected to have taken greater than the assigned dosage.

### 6.4.2. Missed Dose

**RMC-4630:** If a participant misses a dose, it may be taken at the time the omission was discovered provided that it is within 24 hours of the original administration time. Otherwise, the dose should not be administered and should be recorded as an omission. The participant should not administer more than the recommended dose.

**Cobimetinib:** If a dose of COTELLIC is missed or if vomiting occurs when the dose is taken, resume dosing with the next scheduled dose.

#### **RMC-4630 and Cobimetinib: Twice weekly dosing schedule on D1, D2**

If a participant misses a D1 dose of either drug, it should be taken as soon as the missed dose is discovered. The D2 dose should then follow 24-hours after. If the participant misses D2 dose, it should be taken as soon as the missed dose is discovered provided there is at least a 24-hour gap between D1 dose and D2 dose. If the gap between D1 and D2 dose is more than 48 hours, D2 dose should not be administered and should be recorded as an omission. The participant should not administer more than the recommended dose.

#### ***RMC-4630 Twice weekly dosing schedule on D1, D4 and Osimertinib QD (alternative schedule) (Study in US only)***

If a participant misses a dose of RMC-4630, it may be taken at the time the omission was discovered provided that is within 24 hours of the original administration time. Otherwise, the RMC-4630 dose should not be administered and should be recorded as an omission. The participant should not administer more than recommended dose.

If a participant misses a dose of osimertinib, do not make up the missed dose and take the next dose as scheduled

***RMC-4630 Twice weekly dosing schedule on D1, D2 and osimertinib QD (Study in US only)***

If a participant misses a D1 dose of RMC-4630, it should be taken as soon as the missed dose is discovered. The D2 dose should then follow 24-hours after. If the participant misses D2 dose, it should be taken as soon as the missed dose is discovered provided there is at least a 24-hour gap between D1 dose and D2 dose. If the gap between D1 and D2 dose is more than 48 hours, D2 dose should not be administered and should be recorded as an omission. The participant should not administer more than the recommended dose. If a participant misses a dose of osimertinib, do not make up the missed dose and take the next dose as scheduled.

**6.5. Permitted Concomitant Therapy**

Supportive care (eg, antiemetics, analgesics, blood transfusions, hematopoietic growth factor support) may be used at the investigator's discretion and in accordance with institutional procedures. Localized radiotherapy used for palliative purposes may be considered after discussion with the Medical Monitor. Anticoagulation with low-dose aspirin, low-molecular weight heparin (LMWH), and direct Factor-Xa inhibitors are allowed. Contraceptives are also allowed throughout the study as described in [Section 5.1](#).

Antacids are permitted but should not be consumed within 3-4 hours before or after RMC-4630 and cobimetinib or RMC-4630 and osimertinib administration.

Any medication or vaccine, including over-the-counter or prescription medicines, vitamins, and/or herbal supplements, that the participant is receiving at the time of enrollment or receives during the study must be recorded along with the following:

- Reason for use
- Dates of administration including start and end dates
- Dosage information including dose and frequency
- Route of administration

The Medical Monitor should be contacted if there are any questions regarding concomitant or prior therapy.

### 6.5.1. Prohibited Concomitant Therapy

In addition to prohibited medications/foods listed in Exclusion Criteria (Section 5.2), a complete list of prohibited medications during study treatment are provided in this section (Appendix 8).

The following medications are prohibited while on study treatment:

- [REDACTED]
- [REDACTED]
- [REDACTED]
- [REDACTED]
- [REDACTED]
- [REDACTED]
- [REDACTED]
- [REDACTED]
- [REDACTED]

### 6.6. Dose Modification

#### 6.6.1. Dose Modification Rules

A 28-day cycle will be maintained, and dose interruption will be noted in the 28-day cycle schedule.

In the Dose-Escalation cohorts, there will be no dose reductions or modifications during C1, 28-day DLT assessment period unless a DLT has occurred. After C1 and in the Dose-Expansion cohorts, if a dose reduction is recommended, then the combination dose level should be the previous lower dose level considered to be tolerable in prior participants receiving that dose. If the previous lower dose level comprised of two parallel cohorts (ie, two combination dose levels), the investigator and sponsor Medical Monitor may choose one of two lower combination dose level based on the participant’s medical and study drugs history.

- [REDACTED]
- [REDACTED]
- [REDACTED]
- [REDACTED]
- [REDACTED]

[REDACTED]

[REDACTED]

[REDACTED]

Two types of dose modifications are allowed, “dose interruption” and “dose level reduction.” The decision will be per investigator, according to the dose modification criteria and guidelines outlined in [Section 6.6](#). Any allowed dose modification and any deviation from the intended dose (missed doses or overdoses due to participant error) should be documented on the dose electronic Case Report Form (eCRF).

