### 2.3.2. Steps to Minimize Risk

Safety measures to minimize risks to participants have been incorporated in the design of the study. Eligibility criteria specifically exclude patients who may be at increased risk of predictable toxicities.

Safety monitoring (consisting of adverse events assessments, physical examinations, vital signs measurements, ECGs, clinical laboratory tests, Eastern Cooperative Oncology Group (ECOG) performance status, echocardiogram (ECHO)/multigated acquisition (MUGA) scans, and retinal examinations), will occur at regular intervals throughout the study. As a precaution, participants receiving strong CYP3A4 inhibitors ([Appendix 8](#)) and/or inducers are excluded until further data become available.

In addition to dose DLT criteria, dose modifications after the DLT window have been included in order to reduce the risk of toxicity while continuing to provide participants a potential treatment opportunity.

Invasive measures in this study are limited to venipuncture (all study participants) and tumor biopsies in participants when feasible. The primary purpose of the pre-treatment and on-study biopsies is to assess tumor biology and potential response to study intervention. The tumor tissue will also be used to explore predictive biomarkers ([Section 8.7](#)) ([Hirsch 2003](#)).

Two safety committees, a Dose-Escalation and Expansion Committee (“Dose Committee”) and an ISMC, will be used to monitor the safety of RMC-4630 monotherapy, RMC-4630 with cobimetinib combination, and RMC-4630 with osimertinib combination therapy. The Dose Committee is study-specific while the ISMC is RMC-4630 program-specific. The Dose Committee, comprising of Sponsor representatives and investigators, will evaluate the safety data throughout the study and provide recommendations regarding dose levels during the escalation phase as well as decide whether the Dose-Expansion Component may commence at the completion of a given Dose-Escalation Cohort. The ISMC will review emergent safety data at regular intervals for all participants during the course of the trial in conjunction with data from other active RMC-4630 trials. Refer to [Section 8.3.6](#) for details.

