### **6.6.2. Dose Modification Criteria for RMC-4630 and Cobimetinib**

In general, dose adjustments should be based on attribution to a particular drug, if known. Certain adverse events are known to be associated with administration of cobimetinib (cobimetinib IB) whereas others have been observed with the administration of RMC-4630 in clinical or preclinical studies (RMC-4630 IB). [REDACTED]

The following principles apply to Dose Escalation component of the study and should be employed for Grade 3 and certain Grade 4 AEs.

- If the AE is a known toxicity of cobimetinib only, cobimetinib should be interrupted and then dose reduced one level if recovery to  $\leq$ Grade 1 occurs within 28 days. RMC-4630 should be continued at the same dose. However, at the investigator’s discretion, RMC-4630 may be held if the AE does not improve with holding cobimetinib. If the AE does not resolve within 28 days from onset, permanently discontinue cobimetinib.
- If the AE is suspected to be due to RMC-4630, RMC-4630 should be interrupted and then dose reduced one level if recovery to  $\leq$ Grade 1 occurs within 28 days. Cobimetinib should be continued at the same dose. However, at the investigator’s discretion, cobimetinib may be held if the AE does not improve with holding RMC-4630. If the AE does not resolve within 28 days from onset, permanently discontinue RMC-4630.
- If the AE is known for both drugs, hold both drugs until recovery to  $\leq$ Grade 1. Restart at a reduced dose of the drug that was last escalated by one dose level if the recovery to Grade  $<1$  is within 28 days. The second drug may also be dose reduced by one level at the investigator’s discretion and after discussion with the sponsor Medical Monitor.
- If the AE is unknown for either drug, hold both drugs until recovery to  $\leq$ Grade 1. Restart at a reduced the dose of the drug that was last escalated by one dose level if the recovery to grade  $<1$  is within 28 days. The second drug may also be dose reduced by one level at the investigator’s discretion and after discussion with the sponsor Medical Monitor.

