**Table 9      Dose Modification Guidelines for RMC-4630 and Cobimetinib**

[REDACTED]	[REDACTED]
[REDACTED]	[REDACTED]
[REDACTED]	[REDACTED]
[REDACTED]	[REDACTED]
[REDACTED]	[REDACTED]

[REDACTED]	[REDACTED]
[REDACTED]	[REDACTED]
[REDACTED]	[REDACTED]
[REDACTED]	[REDACTED]

[REDACTED]	[REDACTED]
[REDACTED]	[REDACTED]
[REDACTED]	[REDACTED]
[REDACTED]	[REDACTED]

Dose modifications may also occur following the first cycle (DLT assessment period) during the Dose-Escalation Component or Dose-Expansion Component (where applicable) in the following specific instances:

- Any participant who experiences a Grade 3 AE that constitutes a DLT may be considered for dose reduction to last dose cohort upon recovery of the AE to Grade 1 or baseline if deemed medically appropriate by the investigator and Medical Monitor. These participants will be considered to have experienced a DLT at the original dose and, therefore, will not be permitted to remain at the same dose.
  - For participants in the Final Expansion Cohort – if an AE/SAE occurs within the first cycle and meets the DLT definition, participant may dose reduce RMC-4630 to 100 mg D1D2.
- Any participant who experiences a < Grade 3 AE that does not constitute a DLT but that recurs more than once ( $\geq$  Grade 2) after recovering from the initial onset of the AE may be considered for a dose reduction upon recovery of the AE to Grade 1 or baseline if deemed medically appropriate by the investigator and sponsor Medical Monitor. Discontinuation of the study medications after third occurrence of the AE that is Grade 2 (intolerable) or Grade 3.
- Re-challenge at the same or lower dose may be considered after resolution of treatment-related or treatment-unrelated AEs provided the AE did not meet DLT criteria. If the AE recurs, dose modification may be considered.
- Continuation of a single agent RMC-4630 may be allowed if there is presence of, or potential for, clinical benefit as assessed by the investigator and sponsor Medical Monitor. The dose and schedule of RMC-4630 may be cross-referenced to the on-going monotherapy study RMC-4630-01. The options are:

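### Read literally, Section 6.6.1 forbids holding drug for toxicity in Cycle 1 of escalation until a DLT has occurred, which other parts of the protocol contradict

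*Combined protocol and SAP*

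**What the plan says.** Section 6.6.1 sets the Cycle 1 rule for the escalation cohorts: "there will be no dose reductions or modifications during C1, 28-day DLT assessment period unless a DLT has occurred". Later in the same section it explains the term: "Two types of dose modifications are allowed, “dose interruption” and “dose level reduction". The sentence straight after the bar turns to reductions and gives their timing: "After C1 and in the Dose-Expansion cohorts, if a dose reduction is recommended".

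Section 6.6.2 covers the cobimetinib arm. Its scope statement is "The following principles apply to Dose Escalation component of the study and should be employed for Grade 3 and certain Grade 4 AEs". The first principle begins "If the AE is a known toxicity of cobimetinib only, cobimetinib should be interrupted and then dose reduced one level if recovery to", and recovery to Grade 1 or less within 28 days is the condition for restarting at the lower level. Parallel principles cover events attributed to RMC-4630, to both drugs, or to neither known profile; each starts with an interruption or hold. No Cycle 1 limit on these principles is visible.

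Three other parts of the protocol bear on the reading:

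- The DLT lists (4.1.1.2 and 4.2.1.2) include a dose-intensity criterion: a participant who misses about half the planned doses because of drug-related toxicity has a DLT.
- The evaluability rules (4.1.1.3, 4.2.1.3 and Table 15) exclude participants who miss a set number of Cycle 1 doses, but only when the reason is not toxicity.
- Section 2.3.2 describes the modification rules this way: "dose modifications after the DLT window have been included in order to reduce the risk of toxicity".

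**The concern.** The bar covers reductions or modifications, and a modification is either an interruption or a level reduction. On those words a toxicity hold in Cycle 1 is forbidden until a DLT has been met. Many Grade 3 events are not DLTs at onset, so there is a period in which 6.6.1 says not to interrupt while 6.6.2 says to interrupt.

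Two things are at stake. One is safety: a site that follows 6.6.1 to the letter keeps dosing through a Grade 3 toxicity until a duration clock runs out. The other is consistency of the DLT data. DLT incidence is a primary endpoint in both arms, and Table 15 makes the DLT-evaluable set the primary population for the dose-toxicity model. An event that settles during a hold may not settle while dosing continues. Sites that read the rule differently could therefore classify similar events differently, in cohorts as small as three participants.

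**Working it through.** The plan gives no figure to reproduce here. The check is a comparison of text, plus one count of doses.

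**Step 1: when a toxicity is not yet a DLT.** In the cobimetinib arm (4.1.1.2), a Grade 3 non-haematological event counts once it has stayed uncontrolled for more than 72 hours despite maximal supportive care. Grade 3 transaminase or bilirubin elevations count once they persist for more than 5 days. Related events of Grade 4 or higher are DLTs at once, so in this arm the gap concerns Grade 3 events. In the osimertinib arm (4.2.1.2) the clocks are 72 hours, 5 days (rash, hypertension, liver tests) and 7 days (fatigue). Grade 4 neutropenia or thrombocytopenia also counts only after more than 7 days, unless fever or significant bleeding makes it a DLT sooner.

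**Step 2: apply both instructions inside that gap.** Take a cobimetinib-arm escalation participant in Cycle 1 with a Grade 3 rash on its first day. No DLT has occurred, so 6.6.1 read literally bars an interruption. The rash is a Grade 3 event in escalation, so 6.6.2 calls for one. For the osimertinib arm no opposing hold instruction for Cycle 1 is visible, but the 6.6.1 bar is general and reaches that arm's escalation, planned for up to 18 participants (9.2).

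**Step 3: test the literal bar against the dose-intensity criterion.** Planned Cycle 1 doses follow from the schedules: RMC-4630 twice weekly for 4 weeks, 2 × 4 = 8; cobimetinib 21/7, 21; cobimetinib D1, D2, 2 × 4 = 8; osimertinib daily, 28.

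| Drug and schedule | Planned doses | Toxicity misses that make a DLT | Share given at that threshold | Toxicity misses short of it | Other misses that make the participant non-evaluable |
|---|---|---|---|---|---|
| RMC-4630, twice weekly | 8 | 4 | (8 − 4)/8 = 50% | 1 to 3 | 3 |
| Cobimetinib, 21/7 | 21 | 10 | (21 − 10)/21 = 52.4% | 1 to 9 | 6 |
| Cobimetinib, D1, D2 | 8 | 4 | (8 − 4)/8 = 50% | 1 to 3 | 3 |
| Osimertinib, daily | 28 | 14 | (28 − 14)/28 = 50% | 1 to 13 | 8 |

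A criterion that starts at the fourth missed RMC-4630 dose assumes that one, two or three doses can be missed for toxicity without a DLT on that ground. If holds were barred until a DLT had occurred, the criterion would do almost nothing: apart from permanent discontinuation and doses a participant skips unprompted, most toxicity misses would already follow a DLT.

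**Step 4: evaluability.** The last column applies only to doses missed for reasons other than toxicity. Toxicity misses leave the participant evaluable, which again presumes that they occur within the DLT window. Steps 3 and 4 give no hold instruction, so they are evidence of intent rather than a second contradiction.

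**Step 5: reductions.** The continuation of 6.6.1 puts recommended reductions after Cycle 1 or in expansion, and Section 2.3.2 places modifications after the DLT window. Section 6.6.2 does not say otherwise for Cycle 1, so the specific rule can govern. No real conflict remains on reductions.

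**The case against.** The strongest objection is redaction. Bullets and paragraphs are blacked out in 6.6.1 between the bar and the definition of a modification. Text just before the 6.6.2 principles, Table 9, most of 6.6.3 and much of Table 14 are also hidden. An exception for toxicity holds could sit in any of these places. That objection stands: a defect in the full plan is not proven, only one in the visible text.

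A second objection is that nobody would read the bar so strictly. Section 6.6.1 opens by saying that interruptions are noted within the 28-day cycle, with no Cycle 1 exception. Section 6.6.2 leaves management to medical judgement, and Section 8 calls for immediate safety concerns to go to the sponsor at once. This makes continued dosing through severe toxicity unlikely in practice. It does not correct the rule as written: 6.6.1 makes modification decisions subject to the criteria in 6.6, which is where the inconsistency lies.

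Third, Section 6.1.1 already states the dose and schedule for final expansion in the cobimetinib arm, so the 6.6.2 conflict has little left to affect there. This also stands; the forward relevance is mainly the general bar as it applies to osimertinib-arm escalation.

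It might also be said that the list after Table 9 confines modifications to later cycles. It begins "Dose modifications may also occur following the first cycle (DLT assessment period". The word *also* introduces further instances; it does not limit the earlier principles.

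A reader might go further and infer that participants can be reduced in Cycle 1 and still be counted as DLT-free at the assigned dose. The documents do not support that. It would require a site to break the explicit bar on reductions in 6.6.1.

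**Conclusion.** The point holds for interruptions only, and it is minor. On the visible text, 6.6.1 forbids a Cycle 1 toxicity hold before a DLT. That contradicts the hold instruction in 6.6.2 for the cobimetinib arm, and it does not fit the dose-intensity and evaluability rules of either arm.

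The conclusion assumes that *modification* has the same meaning in both sentences of 6.6.1 and that no redacted text supplies an exception. Its numerical size cannot be given: the documents report no Cycle 1 rate of Grade 3 events that fall short of a DLT, so a reader should not infer that the DLT rate or the MTD is biased in a known direction or by a known amount. No sample size or error rate changes. The case for acting is that the correction is nearly free and removes a safety ambiguity from a rule that feeds a primary endpoint.

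**What to change.** In 6.6.1, replace the bar with: *In Cycle 1 of escalation, no dose level reduction is made unless a DLT has occurred; interruption for toxicity is permitted.* This serves both arms.

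In 6.6.2, make the reduction step subject to 6.6.1, and state that a participant who recovers within Cycle 1 from an event that was not a DLT may resume at the assigned level. A new sentence is needed because the existing re-challenge bullet, "Re-challenge at the same or lower dose may be considered after resolution of treatment-related or treatment-unrelated AEs", stands under a lead-in about the period after Cycle 1. Participants who have recovered should not be kept on hold merely to reach Cycle 2. Four missed RMC-4630 doses, which is two weeks at two doses a week, would themselves make a DLT.

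If redacted text already says this, place it beside the bar.

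The cost is one clause and one sentence, with no added participants or procedures. There are two downsides to accept. Some Grade 3 events that resolve during a hold will not count as DLTs, which is how the current duration criteria already work. Long holds can trigger the dose-intensity criterion, because 6.6.2 waits for recovery to Grade 1 or less and allows up to 28 days, as long as the DLT window itself.
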